13.5. Risks to Subjects and Adequacy of Protection Against Risks

Known risks of high dose intravenous vitamin C include oxalate nephropathy that can progress to renal failure and hemolysis in patients with G6PD-deficiency. In an effort to fully avoid these events, patient with primary hyperoxaluria, previous or current oxalate nephropathy, and those with G6PD-deficiency will be excluded from the study.

Based on the reported potential risks of vitamin C, thiamine, and/or hydrocortisone as discussed above (section 3.5), important risks were identified that could be associated with administration of one or all three drugs and have been labeled as "potentially associated adverse events" (PAAE). PAAEs are listed below and will be recorded as detailed in Section 10.6 (Adverse Event Reporting):

Nephrolithiasis
Hemolysis
Hypersensitivity Reactions
Injection Site Reactions

Note: Individual cases of events that occur commonly based on the natural history of severe sepsis (e.g. acute kidney injury) and/or the treatments commonly administered as part of routine sepsis care such as steroids (e.g. adrenal insufficiency) will not be reported as PAAEs, but rather reviewed in aggregate at regular quarterly intervals by the DCC and DSMB to identify any potential effects related to the study intervention, with procedures for stopping in accordance with the DSMB charter.

Point of Care Glucometry – As discussed in section 3.5, there is a risk that some point of care glucometers could give falsely elevated readings when serum vitamin C concentrations are high. Therefore, participating sites will be required to use only point of care devices (Nova StatStrip), or central or critical care laboratory devices that have been validated for use during high dose intravenous vitamin C.

Further, participating sites using a StatStrip device for glucose monitoring will confirm serum glucose measurements using a central or critical care laboratory device before initiating insulin therapy, and for (or up to) 24 hours after study drug is completed (for patients who are not already on insulin therapy). Following initiation of insulin therapy, regular correlation of StatStrip and central or critical care glucose measurements will be performed daily with routine labs (this applies as well to patients who were already on insulin therapy, prior to study drug initiation). Consistent with standard of care, if the clinical team or site investigator believes a StatStrip measurement is erroneous or suspects symptomatic hypoglycemia, a confirmatory serum sample should be measured by a central or critical care laboratory.

Subject Confidentiality – All data (case report forms, recordings, laboratory specimens, imaging, and other records) kept at the site will be physically and electronically secured to maintain subject confidentiality. Paper records with subject data will be stored in locked office or cabinet. Computer records will always be password protected, and encrypted when possible. The study database is maintained behind a secure firewall, access is password protected and it uses SSL encryption for all data entry and access.

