3.5. Risk/Benefit Assessment

Vitamin C

High dose intravenous vitamin C has been in clinical use for more than half a century,^{59,60} and is known to have few toxic or adverse effects.^{23,61} In one study of 9,227 patients receiving an average of 24 g intravenous vitamin C every four days, only 59 adverse events were reported.⁶² Among these, the most common were lethargy and fatigue. Others included irritation at the infusion site, nephrolithiasis, hyperglycemia, nausea, two cases of hemolysis, and one case of renal failure in a patient with pre-existing kidney disease and cancer metastatic to the kidneys.

Other adverse effects that have been reported are also rare, and are mild with two exceptions: oxalate nephropathy and hemolysis. Oxalate is a metabolite of vitamin C. At high concentrations, it can deposit in the kidneys leading to oxalate nephropathy. This has been reported among individuals who either (1)

received grams per hour of intravenous vitamin C,⁶³⁻⁶⁶ or (2) received moderate to high doses of oral vitamin C for weeks to months.⁶⁷⁻⁷¹ Despite these case reports, three recent studies of high dose intravenous vitamin C have showed either similar or reduced renal failure event rates among patients with sepsis or burn injury, compared to patients that did not receive vitamin C.^{20,37-39} Acute hemolysis in the setting of high dose intravenous vitamin C administration is also rare and is only known to occur in patients with G6PD-deficiency.⁷²⁻⁷⁴

Because oxalate nephropathy and hemolysis are rare events, and because patients with primary hyperoxaluria, previous or current oxalate nephropathy, and those with known G6PD-deficiency will be excluded from the study, we do not view these potential adverse events as significant risks to enrolled patients. Moreover, given the high prevalence and mortality associated with sepsis, the benefit of identifying an effective pharmacologic therapy for the sepsis syndrome justifies the small risk that one of these rare adverse events could occur.

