10.4. Clinical Assessments and Procedures

Baseline Data - At enrollment, basic information about disease characteristics and the subject, including common sepsis and research related variables will be collected. Examples include:

- Demographics
 - Age
 - Race/Ethnicity
 - o Gender
 - Education
- Anthropometrics
- Source of Admission
- Comorbidities and Medical History
- History and Physical (brief physical exam findings)
- APACHE II (ICU mortality) using the most aberrant data from the 24 hours preceding the time of randomization

- SOFA Score
- Vasopressor requirements
- Respiratory and ventilator support requirements
- Total volume of fluid resuscitation
- Presumed infection source and organism
- Initial antimicrobial therapy
- CAM-ICU

Daily Measurements and Physiologic Data:

Use data that is obtained as close to 8 a.m. each day while the patient is in the ICU up to day 5.

- Vital Signs (MAP, HR, RR, and Temp)
- CAM-ICU Score
- SOFA Score
- Study Drug Compliance

Additional Measures to be determined and collected at time of ICU discharge and/or Hospital Discharge:

- Daily Vasopressor Requirements
- Daily Ventilator / Respiratory Support Requirements
- Antimicrobial therapy
- Final infectious source data
- Location and/or disposition

Outcome Assessments – The primary outcome measure is VVFD at 30 days (+/-3 days) after randomization. Vasopressor and ventilator-free days will be determined by recording all start and stop days of these measures. Additional measures will include renal replacement therapy (RRT) free days and determination of subject's vital status. These will be assessed at ICU discharge, and hospital discharge or day 30 (whichever comes first). The final study visit for individual sites will be the time of hospital discharge or day 30 (whichever comes first). For patients discharged prior to day 30, status at discharge will be assumed to reflect outcome at day 30.

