Potentially Associated Adverse Events (PAAE): Based on the reported potential risks of vitamin C, thiamine, and/or hydrocortisone, several important risks have been identified that could be associated with administration of one or all three drugs and have been labeled as "potentially associated adverse events" (PAAE). All PAAEs occurring following randomization through the initial hospital stay will be recorded on the AE page in the EDC portal. Identified PAAEs include but are not limited to nephrolithiasis, hemolysis, (refer to **Section 13.5 Table** for a detailed list).

Serious Adverse Event: A serious adverse event (SAE) is an AE that occurs during the study (ie, after randomization through to hospital discharge or day 30 follow-up [whichever occurs first]), that fulfills one or more of the following criteria:

- 1. Results in death (for the purposes of this trial, deaths will be captured as clinical outcomes and only recorded as an SAE if deemed related to the investigational product)
- 2. Is life-threatening (places the subject at immediate risk of death from the event as it occurred)
- 3. Results in inpatient hospitalization or prolongation of an existing hospitalization
- 4. Results in a persistent or significant disability/incapacity
- 5. Results in a congenital anomaly/birth defect; OR
- 6. Is an important and significant medical event. (Based upon appropriate medical judgment, may jeopardize the subject's health and may require medical or surgical intervention to prevent one of the other outcomes listed in this definition).

Serious and Unexpected Adverse Event

Serious Adverse Events (see above) that are **Unexpected** (i.e. not consistent with the natural history of the disease under study) and deemed to be definitely or possibly study-related will be reported in an expedited manner to the DSMB (see **Reporting Rules** below).

Relationship to Investigational Product

Determination of the relationships between AEs and administration of Investigational Product is a clinical decision based on all available information at the time of the completion of the EDC. Research relatedness will be evaluated according to the following definitions:

UNRELATED	The temporal relationship between treatment exposure and the adverse event is unreasonable or incompatible and/or adverse event is clearly due to extraneous causes (e.g., underlying disease, environment)

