11.4.4. Safety Endpoints

Complete listings and summary tables for all safety information will be presented for subjects who are included in the Safety analysis set. Descriptive statistics (number and percentage) for adverse events and serious adverse events will be presented by treatment arm. No formal statistical analysis will be performed.

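### Oxalate nephropathy is one of two non-mild vitamin C harms the protocol names, but it is not a listed PAAE, and no by-arm renal safety table is named

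*Combined protocol and SAP*

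**What the plan says.** **Named risks.** Section 3.5 says that other reported vitamin C effects "are mild with two exceptions: oxalate nephropathy and hemolysis". Section 13.5 repeats the pair: "Known risks of high dose intravenous vitamin C include oxalate nephropathy that can progress to renal failure and hemolysis in patients with G6PD-deficiency".

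**PAAE list.** Section 13.5 presents PAAEs as the important risks identified from the discussion in 3.5. It lists nephrolithiasis, hemolysis, hypersensitivity reactions and injection site reactions. Section 10.6 is looser ("Identified PAAEs include but are not limited to nephrolithiasis, hemolysis") but sends the reader to the 13.5 table for detail.

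**AKI.** A note in 13.5 says that individual cases of events common in severe sepsis, with AKI as the example, "will not be reported as PAAEs, but rather reviewed in aggregate at regular quarterly intervals by the DCC and DSMB". Stopping procedures for that review are left to the DSMB charter.

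**Other routes (10.6).** An expected event counts as a study-related AE only if the investigator considers it related or it leads to discontinuation of study drug. Related non-serious AEs are recorded for the first 5 days. Sites enter SAEs that are both unexpected and study related, to discharge or day 30.

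**Renal data collected.** Section 10.4: "Additional measures will include renal replacement therapy (RRT) free days and determination of subject's vital status". Sections 10.2 and 10.3 have creatinine recorded if available, near 8 a.m., to day 5 or ICU discharge.

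**Analysis.** Section 11.4.4 promises listings and tables of safety information in general, then becomes specific: "Descriptive statistics (number and percentage) for adverse events and serious adverse events will be presented by treatment arm". No renal variable is named there, in Section 5 or in 11.4.3.

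**The concern.** The two harms singled out as not mild are handled differently. Hemolysis is a PAAE, recorded whatever its presumed cause through the hospital stay. Oxalate nephropathy is not on the list. Its likely clinical picture in a septic patient is AKI, and that is expressly removed from PAAE reporting.

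What remains is a filter based on attribution. Where sepsis is a ready explanation for kidney injury, a blinded investigator has little basis for attributing a case to study drug, so a by-arm table built on attributed events may miss most of a real excess. The exclusion criteria remove patients with known predisposition or previous disease. They do not prevent new cases.

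At stake is the trial's reported conclusion on a risk it names itself. The objective renal measures that could answer the question are being collected, but the plan does not commit to showing them by arm. The reference study's lower RRT requirement (3.3, p = 0.02) adds interest, although confirming it is not a stated objective.

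**Working it through.** The plan states no renal safety figure, so there is none to reproduce. The check is a trace through the text, followed by an illustration of precision.

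**1. Trace of each event**

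| Event | On the PAAE list (13.5)? | Route to the AE/SAE tables |
|---|---|---|
| Hemolysis | Yes | All cases, randomization through hospital stay |
| Oxalate nephropathy, diagnosed | No | If judged related: non-serious to day 5; serious and unexpected to discharge or day 30 |
| AKI judged related, or leading to discontinuation | No (excluded by the note) | Study-related AE under 10.6 |
| AKI attributed to sepsis | No (excluded by the note) | None stated; aggregate DCC and DSMB review only |

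The SAE route is narrow for AKI. Section 10.6 defines an unexpected event by inconsistency with the natural history of the disease, and 13.5 describes AKI as common in that natural history. Serious AKI would therefore be read as expected.

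**2. Trace of each renal variable**

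| Variable | Collected | Named in Section 5, 11.4.3 or 11.4.4? |
|---|---|---|
| RRT-free days | Hospital discharge or day 30 (10.2, 10.4) | No |
| Creatinine | If available, to day 5 or ICU discharge (10.2, 10.3) | No |

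A table made under the general wording would also need choices that the plan leaves open. Section 11.1 groups by randomized arm, while the safety set in 11.3.3 groups by treatment received. The worst-value rule for deaths in 10.5 covers primary and secondary endpoints, and RRT-free days is neither.

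**3. What a by-arm table would deliver**

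Inputs: 250 per arm, from the initial target of 500 randomized 1:1 (6.3). The control event rate p is an assumption, because the documents give none.

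Formula: half-width = 1.96 × √(2p(1−p)/n).

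- p = 5%: 1.96 × √(2 × 0.05 × 0.95/250) = 3.8 points
- p = 10%: 1.96 × √(2 × 0.10 × 0.90/250) = 5.3 points
- p = 20%: 1.96 × √(2 × 0.20 × 0.80/250) = 7.0 points

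At the maximum of 2000 (1000 per arm), the same formula gives 1.9, 2.6 and 3.5 points.

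**4. What listing oxalate nephropathy could yield**

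Probability of at least one case among 250 treated = 1 − (1 − r)^250, for an assumed true rate r:

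- r = 0.2%: 0.39
- r = 0.5%: 0.71
- r = 1%: 0.92

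These are chances that a case occurs, not that it is diagnosed.

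**The case against.** The strongest reply is that the plan already covers this. Section 11.4.4 promises tables of safety information without restriction, and 11.1 has continuous variables summarized by arm unless otherwise specified. A reader might infer from the by-arm sentence alone that the trial can say nothing by arm about renal harm. The documents do not support that: a renal table is permitted. It is not promised, however, and its grouping, death rule and missing-data display are undefined.

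A reader might also infer that AKI is never reported individually. That is too strong. It is excluded as a PAAE, but AKI judged related or leading to discontinuation can still be recorded. A diagnosed case of oxalate nephropathy, if serious and judged related, fits the SAE rule, and the wording in 10.6 does not close the PAAE list. Section 13.2 also promises that serious events go to the single IRB regardless of causality. That promise does not match the site entry rule in 10.6, and the two need reconciling.

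Nor is renal injury unmonitored. The aggregate review in 13.5 looks for effects of the intervention, and closed DSMB sessions may see data by arm (13.4). Whether renal stopping criteria exist cannot be judged without the charter. This protects participants during the trial, but nothing carries the review into the final analysis.

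The objection also limits the remedy. Neither 10.2 nor 10.4 shows a field for chronic RRT at baseline. A value taken near 8 a.m. is not a true peak creatinine. Scoring deaths as zero RRT-free days would mix mortality into a renal measure.

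**Conclusion.** The concern stands as a gap in recording and reporting. Oxalate nephropathy is missing from a list that 13.5 describes as holding the important risks from 3.5. AKI attributed to sepsis has no stated route to the only events named by arm. The collected renal data are not assigned to any analysis. It does not touch the primary analysis, and the plan does not forbid a renal comparison.

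The number of events lost to the attribution filter cannot be computed from the documents. That it could be most of them is a judgement about blinded attribution in sepsis. What can be shown is the precision available: about ±3.8 to ±7.0 points at 250 per arm, over assumed control rates of 5% to 20%. That calculation takes equal rates in both arms and complete data. Incomplete creatinine would widen the intervals for any creatinine-based event.

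**What to change.** 1. Add oxalate nephropathy to the PAAE list in 13.5.
2. In 11.4.4, name one descriptive by-arm table on the safety set, made regardless of investigator attribution, with:
   - any RRT use and RRT-free days, to discharge or day 30;
   - highest recorded creatinine to day 5 or ICU discharge, relative to baseline;
   - risk differences with 95% intervals for the binary items, and no formal test.
3. Present RRT-free days with deaths scored zero and also with deaths shown separately, so that a mortality difference does not mask a renal one.
4. Split out patients on chronic RRT only if the baseline history already records it.
5. Show counts of missing creatinine by arm and by day.
6. Reconcile the SAE scope in 10.6 with the IRB reporting promise in 13.2.

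The main additions cost one line in the PAAE list and one safety table, with no new tests or visits. Before finalizing, check that the case report form allows any RRT use to be derived for patients who die, because the schedule shows only RRT-free days. The main weakness is that creatinine is collected only if available and stops at day 5 or ICU discharge, so later injury is seen only through RRT.

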13.6. Potential Benefit of the Research to Subjects and Others

There is equipoise regarding whether the TP will lower mortality and affect other important outcomes among patients with sepsis. Although preliminary published evidence suggests such a benefit, it is not guaranteed that specific benefit will be gained from participation in this study.

13.7. Importance of the Knowledge to be Gained

There are no specific medical therapies available that have been shown to improve the outcomes of patients with sepsis. The purpose of the current study is to determine (or confirm) the efficacy of the TP in the management of patients with circulatory and/or respiratory dysfunction resulting from sepsis. Therefore, the conduct of this trial may substantially expand and improve the available therapeutic options for the treatment of sepsis.

13.8. Data and Safety Monitoring Plan

The study will be monitored at regular intervals by the DCC and/or DSMB as specific in the DSMB Charter. Monitoring will be conducted in accordance with GCP guidelines. Investigators must allow monitors or other relevant health authorities to inspect facilities and records relevant to the study.

14.Regulatory Compliance

14.1. Investigator responsibilities

Each Site Investigator agrees to:

- 1. Conduct the study in accordance with the protocol and only make changes after notifying the SIRB, except when to protect the safety, rights or welfare of subjects.
- 2. Personally conduct or supervise the study (or investigation) at their site.
- 3. Ensure that the requirements relating to obtaining informed consent and IRB review and approval meet federal guidelines, as stated in § 21 CFR, parts 50 and 56.
- 4. Report to the study team and CCC any AEs that occur in the course of the study, in accordance with §21 CFR 312.64.
- 5. Ensure that all associates, colleagues and employees assisting in the conduct of the study are informed about their obligations in meeting the above commitments.
- 6. Maintain adequate and accurate records in accordance with §21 CFR 312.62 and to make those records available for inspection by the DSMB.
- 7. Ensure that an IRB that complies with the requirements of §21 CFR part 56 will be responsible for initial and continuing review and approval of the clinical study.
- 8. Promptly report to the IRB and the study team and clinical coordinating center, all changes in the research activity and all unanticipated problems involving risks to subjects or others (to include protocol amendments).
- 9. Seek IRB approval before any changes are made in the research study, except when necessary to eliminate hazards to the patients/subjects.
- 10. Comply with all other requirements regarding the obligations of clinical investigators and all other pertinent requirements listed in § 21 CFR part 312.

14.2. Publications and data sharing

The preparation and submittal for publication of manuscripts containing the study results shall be in accordance with a process determined by mutual written agreement among the VICTAS PIs and participating institutions. The publication or presentation of any study results shall comply with all applicable privacy laws, including, but not limited to, the Health Insurance Portability and Accountability Act of 1996.

Methylprednisolone	4	12-36	
Prednisolone	5	12-36	
Prednisone	5	12-36	
Triamcinolone	4	12-36	
Long-Acting			
Betamethasone	0.75	36-72	
Dexamethasone	0.75	36-72	

